### 1.3 SCHEDULE OF ACTIVITIES

**Table 1: Schedule of Activities**

Procedures	Enrollment	24 months post-enrollment
Informed Consent	x	
Intake Information	x	
Patient Questionnaire	x	
Adverse Childhood Experiences (ACEs) Questionnaire	x	
Secondary Data Pull		x*

\*Secondary data are pulled at a coordinated time point at which data reflecting 24 months post-enrollment was provided for each study participant.

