## 9 STATISTICAL CONSIDERATIONS

## 9.1 STATISTICAL HYPOTHESES

Primary Endpoint:

- Overdose Admissions
  - [Measured: 1 year pre-enrollment through 1 year post-enrollment]

We hypothesize that, compared to patients in the control condition, patients receiving the POINT intervention will experience fewer subsequent admissions to the ED for overdose.

Secondary Endpoints:

- MOUD Engagement
  - [Measured: 1 year pre-enrollment through 1 year post-enrollment]
- Duration of MOUD Engagement
  - [Measured: 1 year pre-enrollment through 1 year post-enrollment]
- ED Admissions
  - [Measured: 1 year pre-enrollment through 1 year post-enrollment]
- Inpatient Hospital Admissions
  - [Measured: 1 year pre-enrollment through 1 year post-enrollment]
- Time to Relapse
  - [Measured: Enrollment through 1 year post-enrollment]
- Medicaid Enrollment for Participants Without Insurance
  - [Measured: Enrollment through 1 year post-enrollment]
- Child Welfare Involvement
  - [Measured: 3 years pre-enrollment through 1 year post-enrollment]
- Incarceration
  - [Measured: 3 years pre-enrollment through 1 year post-enrollment]

We hypothesize that, compared to patients in the control condition, patients receiving the POINT intervention will experience better recovery outcomes (i.e., higher MOUD engagement and longer duration of engagement, lower ED and inpatient admissions, longer times between relapse, higher Medicaid enrollment for those without insurance, lower child welfare involvement, and lower incarceration).

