### 9.4 STATISTICAL ANALYSES

#### 9.4.1 GENERAL APPROACH

We will summarize patient characteristics using means and standard deviations for continuous variables and counts and proportions for categorical variables. Initial analysis of outcomes (using data pulled at 9 months) will focus on MOUD engagement one-month post overdose, as all other outcomes will be too distal to observe any meaningful change. This time period is based on our prior POINT experience demonstrating initial engagement tends to happen within 1-2 weeks of overdose. We will focus on immediate outcomes (e.g., treatment engagement, length, dropout). While observed change in more distal outcomes (e.g., subsequent overdose and mortality) is unlikely to be seen in such a short pilot period, we will look at them and, if needed, adjust the benchmark (established based on our experience at Eskenazi) for the power analysis. Summary of outcome measures will be computed similarly. The 95% confidence intervals of outcome measures for the POINT and standard care arms will be used to estimate the rate of binary outcomes and mean of continuous outcomes.

The primary analysis involves comparison of outcome measures post ED discharge between the POINT and standard care arms. Binary outcome measures (e.g., MOUD engagement and dropout, subsequent overdose, overdose mortality, and all-cause mortality) will be compared between the POINT and standard care arms using the Fisher's exact test. Length of MOUD treatment will be compared using the Wilcoxon rank sum test. Comparison of the length of time to relapse will be conducted using the survival analysis. Time to relapse will be plotted using the Kaplan Meier curve and comparison between the POINT and standard care arms will be performed using the log rank test.

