#### 9.4.3 ANALYSIS OF THE SECONDARY ENDPOINT(S)

Secondary endpoints	
Note if analysis of secondary endpoint(s) are dependent on findings of primary endpoint	Analysis of secondary endpoints are not dependent on the findings of primary endpoint.
Describe how each secondary endpoint is calculated, if not readily apparent	
Change in MOUD Engagement: Using state methadone treatment data, Medicaid claims data, state prescription drug monitoring data, and electronic health records data to identify whether or not the person engaged in at least one episode of MOUD treatment (methadone, buprenorphine, or naltrexone) within the specified time period.
 
Change in MOUD Engagement Duration: Using state methadone treatment data, Medicaid claims data, state prescription drug monitoring data, and electronic health records data to calculate the number of days MOUD treatment was received during the specified time period.
 
Change in ED Admissions: Using electronic health records, it is calculated as the total combined number of all-cause ED presentation within the specified time period.
 
Change in Inpatient Hospital Admissions: Using electronic health records, it is calculated as the total combined number of all-cause hospital admissions within the specified time period.
 
Time to Relapse: Using electronic health records data, it is calculated as number of days to the first overdose ED visit or overdose death since the index ED. Subjects who did not experience overdose ED or overdose death are censored at the end of the specified time period or the time of death due to other reasons, whichever occurred first
 
Change in Medicaid Enrollment for Participants Without Insurance: Using Medicaid claims data to identify Medicaid coverage among participants within the specific time period.

	
Change in Child Welfare Involvement: Using child welfare data to identify the number of new cases and children removed from the home within the specified time period.
 
Change in Incarceration: Using public incarceration data to identify the number of days of incarceration within the specific time period.

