
Describe the scale (nominal/binary/categorical, ordinal, and interval); state if it is measured as a single endpoint/summary measure or repeated measure
	
Change in MOUD Engagement: binary
 
Change in MOUD Engagement Duration: Interval/Ratio
 
Change in ED Admissions: binary
 
Change in Inpatient Hospital Admissions: binary
 
Time to Relapse: Interval
 
Change in Medicaid Enrollment for Participants Without Insurance: Binary
 
Change in Child Welfare Involvement: binary
 
Change in Incarceration: Interval

Describe the statistical procedure(s) that will be used to analyze the secondary endpoint (e.g., multiple regression, mediation or moderation analyses, multilevel modeling, MANOVA). Describe the covariates and factors in the model. Provide rationale for covariates and how they will be selected to achieve a parsimonious model. If decision to specify covariates is deferred for the SAP, indicate here.
	
We will summarize patient characteristics using means and standard deviations for continuous variables and counts and proportions for categorical variables. The primary analysis involves comparison of outcome measures post ED discharge between the POINT and standard care arms. Binary outcome measures (e.g., MOUD engagement, subsequent overdose, overdose mortality, and all-cause mortality) will be compared between the POINT and standard care arms using the Fisher's exact test. Length of MOUD treatment will be compared using the Wilcoxon rank sum test. Comparison of the length of time to relapse will be conducted using the survival analysis. Time to relapse will be plotted using the Kaplan Meier curve and comparison between the POINT and standard care arms will be performed using the log rank test.

Describe how results of statistical procedure(s) will be presented (e.g., adjusted means (Least-squares means (LSMEANS)) with standard errors or effect size
	
For continuous endpoints, we will present the mean and standard deviation or median and interquartile range for each treatment arm.

	Frequency and percentages are presented for binary endpoints. Time to event endpoints are presented using estimated survival probability at the end of the specified time period.

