Describe details to check assumptions required for certain types of analyses (e.g., checks on assumptions of normality, transformations or, when appropriate, nonparametric tests)	Nonparametric tests are used to compare endpoints between treatment arms. Fisher's exact test is used for binary variables, Wilcoxon rank sum test is used for continuous variables, and log-rank test is used for time to event variables.
Describe the Populations for which the analysis will be conducted as discussed in Section 9.3, Populations for Analyses	All study participants
Describe how missing data will be handled (e.g., type of imputation technique, if any, and provide justification), and approach to handling outliers, non-adherence and lost to follow-up	We do not expect there to be missing data due to the use of administrative datasets.
If there is more than one primary endpoint or more than one analysis of a particular endpoint, state the statistical adjustment used for Type I error criteria or give reasons why it was considered unnecessary	Not relevant as there is only one primary endpoint and each endpoint is analyzed once.

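### Time to Relapse is summarised by a one-year Kaplan-Meier probability that censors other-cause deaths, so it overstates the proportion who relapse in any arm where such deaths precede later relapses; the effect is small and a cumulative incidence estimate removes it

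*Combined protocol and SAP*

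**What the plan says.** Section 9.4.3 defines Time to Relapse as the "number of days to the first overdose ED visit or overdose death since the index ED". Overdose deaths are therefore events. People with no event "are censored at the end of the specified time period or the time of death due to other reasons, whichever occurred first". Section 9.1 sets the window: "Measured: Enrollment through 1 year post-enrollment".

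Section 9.4.1 names the estimator: "Time to relapse will be plotted using the Kaplan Meier curve". Section 9.4.3 names the test ("log-rank test is used for time to event variables") and the absolute summary: "Time to event endpoints are presented using estimated survival probability at the end of the specified time period". Section 9.4.1 adds a covariate-adjusted Cox model.

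On completeness of follow-up, the footnote to Table 1 (section 1.3) says that "data reflecting 24 months post-enrollment was provided for each study participant", and section 9.4.3 expects no missing data for the secondary endpoints.

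No cumulative incidence or competing-risk method appears anywhere. The only death-related sensitivity analysis, in 9.4.2, belongs to the primary endpoint and drops those who die.

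**The concern.** Someone who dies of another cause can no longer overdose. Kaplan-Meier treats that person as still at risk but unobserved, and passes their weight to those who remain. One minus the curve then estimates a net risk, that is, the relapse risk if other deaths were abolished and the dead would have relapsed at the survivors' rate. It does not estimate the proportion of the arm who relapse within the year.

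Kaplan-Meier is useful when follow-up is incomplete for administrative reasons. That need does not arise here: everyone has data well past 12 months, so the only early censoring the rule creates is other-cause death. The estimator departs from a simple proportion only through the handling of those deaths.

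At stake is the absolute one-year risk that readers will take from this endpoint. In a pragmatic trial meant to show effectiveness under real-world conditions, they will naturally read it as the share of patients who relapse.

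**Working it through.** **Inputs from the documents.** Event, censoring rule, estimator, test, summary and one-year window as above. Planning rate of subsequent overdose under standard care 12%, and a 6-point reduction, giving 6% under POINT (section 9.2). 356 per arm, 80% power, 5% level (section 9.2).

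**Input not in the documents.** The one-year probability of other-cause death, D. I take 1%, 3%, 5% and 10%.

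**The plan's own figure.** The documents give no number for Time to Relapse. The sample size confirms that 12% and 6% are the rates in use. With pooled variance, two-sided 5% and no continuity correction:

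n = [1.960 × √(2 × 0.09 × 0.91) + 0.842 × √(0.12 × 0.88 + 0.06 × 0.94)]² / 0.06² = 356 per arm, as stated.

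**Direction.** With no other censoring before one year, the Aalen-Johansen estimate at one year is the number who relapse divided by the number in the arm. Kaplan-Meier removes each other-cause death from later risk sets, so every later relapse counts for more. One minus Kaplan-Meier is therefore larger whenever a relapse follows such a death, and equal otherwise.

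**Size.** Let F be the one-year value of one minus Kaplan-Meier. Under constant cause-specific hazards:

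- h1 = −ln(1 − F) for relapse, and h2 = −ln(1 − D) for other-cause death.
- Cumulative incidence = h1/(h1 + h2) × [1 − exp(−(h1 + h2))].

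For F = 0.12 and D = 0.05: h1 = 0.1278, h2 = 0.0513, and 1 − 0.88 × 0.95 = 0.164. Cumulative incidence = 0.1278/0.1791 × 0.164 = 0.1170, so the overstatement is 12.00 − 11.70 = 0.30 points. A simulation of 2 million subjects gave 11.7%.

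| D | Cumulative incidence when F = 12% | Overstated by | Cumulative incidence when F = 6% | Overstated by | Arm difference (6.00 by Kaplan-Meier) |
|---|---|---|---|---|---|
| 1% | 11.94% | 0.06 | 5.97% | 0.03 | 5.97 |
| 3% | 11.82% | 0.18 | 5.91% | 0.09 | 5.91 |
| 5% | 11.70% | 0.30 | 5.85% | 0.15 | 5.85 |
| 10% | 11.40% | 0.60 | 5.70% | 0.30 | 5.70 |

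**Unequal mortality.** With D = 5% in control and 2% in POINT, the difference is 11.70 − 5.94 = 5.76 points. With the rates reversed it is 11.88 − 5.85 = 6.03 points.

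**More frequent relapse.** If F is 30%, the overstatement is 0.28, 0.71 and 1.44 points at D = 2%, 5% and 10%.

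**Timing.** Constant hazards give a middle case. If 12% of an arm relapse, 5% die of other causes, and every such death comes before the first relapse, one minus Kaplan-Meier is 0.12/0.95 = 12.63%, an excess of 0.63 points. If every such death comes after the last relapse, the excess is zero.

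**The case against.** The strongest reply is that the censoring rule is explicit and prespecified, that a net risk is a coherent quantity under independent censoring, and that the plan never calls its survival probability the proportion who relapse. This stands in part: nothing is miscalculated, but the plan does not say that a net risk is intended, and that is not the natural quantity for a real-world question.

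A second reply is size. At 356 per arm the 95% half-width around 12% is 1.96 × √(0.12 × 0.88/356) = 3.4 points, and around the 6-point difference about 4.2 points. Sections 1.2 and 9.2 record that enrollment fell short, so actual intervals are wider. An error of 0.06 to 0.60 points would change no conclusion. This stands, and it is why the point is minor.

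A third reply is that overdose and all-cause mortality are compared by arm with Fisher's exact test (9.4.1, 9.4.3), so readers could judge the amount of competing mortality. They could, but those comparisons do not correct the reported probability.

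Four stronger readings are tempting and not supported:

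- **Overstatement is certain in both arms.** It needs other-cause deaths followed by relapses in that arm. Section 8.3.3.3 lists all-cause mortality as expected in the adverse-event sense but gives no rate. At 1%, about 4 deaths per arm would be involved at the planned size (0.01 × 356 = 3.6), and an under-enrolled arm might have none.
- **The result will conflict with the primary endpoint's percentages.** Section 9.4.2 does not say how the main analysis counts people who die. The endpoints also differ by definition, since only Time to Relapse includes overdose death, so they could disagree without any competing-risk effect.
- **The one-year probability is the only summary of this endpoint.** The curve, the log-rank test and an adjusted Cox model are also planned.
- **The treatment comparison is invalid.** Log-rank and Cox compare the cause-specific hazard of relapse, and censoring other-cause deaths is the standard handling for that.

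**Conclusion.** The point holds for the absolute one-year figure only. Under the plan's rule, other-cause death is the sole source of censoring before one year, so one minus Kaplan-Meier overstates the proportion who relapse in any arm where such a death precedes a later relapse. The error runs in one direction.

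It is small: about 0.06 to 0.60 points at a 12% Kaplan-Meier risk, with the arm difference hardly moved. These figures assume 1% to 10% other-cause mortality, which the documents do not supply, and constant hazards. They also take the footnote on 24-month data at face value. The error would grow with more frequent relapse, higher mortality or deaths concentrated early. No between-arm test is affected.

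**What to change.** In 9.4.1 and 9.4.3, make the one-year Aalen-Johansen cumulative incidence of relapse the absolute-risk summary, by arm and with a 95% confidence interval. Treat death from other causes as a competing event and show its cumulative incidence alongside. Label the log-rank test and Cox model as cause-specific comparisons.

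The note in 9.2 speaks of the planned analyses in the past tense. If the Time to Relapse analysis is already done, keep the prespecified Kaplan-Meier figure, label it a net risk that censors other-cause deaths, and add the cumulative incidence next to it as an additional estimate. That avoids replacing a prespecified summary after the fact.

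The cost is a sentence or two and a standard procedure on the same data. The censoring rule already requires cause of death, and section 8.1 already lists state vital records as a source. The tests, the endpoint definition and the sample size do not change.

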#### 9.4.4 SAFETY ANALYSES

Not applicable.

#### 9.4.5 BASELINE DESCRIPTIVE STATISTICS

Baseline characteristics will be calculated and compared to assess if there are any significant differences between groups.

#### 9.4.6 PLANNED INTERIM ANALYSES

Because the availability of data from administrative sources is outside the control of the research team, interim analyses could not be planned for.

#### 9.4.7 SUB-GROUP ANALYSES

No sub-group analyses are planned for this study.

#### 9.4.8 TABULATION OF INDIVIDUAL PARTICIPANT DATA

Individual participant data by measure and time point will not be listed.

#### 9.4.9 EXPLORATORY ANALYSES

No exploratory analyses are planned for this study.

## 10 SUPPORTING DOCUMENTATION AND OPERATIONAL CONSIDERATIONS

### 10.1 REGULATORY, ETHICAL, AND STUDY OVERSIGHT CONSIDERATIONS

#### 10.1.1 INFORMED CONSENT PROCESS

##### 10.1.1.1 CONSENT/ASSENT AND OTHER INFORMATIONAL DOCUMENTS PROVIDED TO PARTICIPANTS

Consent forms describing in detail the study intervention, study procedures, and risks will be given to the participant and written documentation of informed consent will be completed prior to starting the study intervention. The following consent materials are submitted with this protocol: (1) consent form, (2) list of competency questions, (3) health information release form.

##### 10.1.1.2 CONSENT PROCEDURES AND DOCUMENTATION

Once the patient is determined to meet all the initial eligibility criteria, the research team member will begin informed consent. Informed consent is a process that is initiated prior to the individual's agreeing to participate in the study and continues throughout the individual's study participation. Consent forms will be Institutional Review Board (IRB)-approved and the participant will be read the document by a recovery coach or research assistant and review the document. The study team member will explain the research study to the participant and answer any questions that may arise. A verbal explanation will be provided in terms suited to the participant's comprehension of the purposes, procedures, and potential risks of the study and of their rights as research participants.

We will not fully disclose the purposes of the research to the standard care arm because (1) Methodist Hospital and Ball Memorial were planning on implementing POINT outside of the context of this study and because their ability to staff recovery coaches is limited anyway, we are not creating any disparity in patients ability to access point that would not naturally exist and (2) we are concerned that full disclosure of the purposes would unnecessarily upset the control arm patients who might desire the services after learning of them.

Participants will have the opportunity to carefully review the written consent form and ask questions prior to signing. The participant will sign the informed consent document prior to data collection beginning. Participants must be informed that participation is voluntary and that they may withdraw from the study at any time, without prejudice. A copy of the informed consent document will be given to the participants for their records. The rights and welfare of the participants will be protected by emphasizing to them that the quality of their medical care will not be adversely affected if they decline to participate in this study.

##### 10.1.2 STUDY DISCONTINUATION AND CLOSURE

This study may be temporarily suspended or prematurely terminated if there is sufficient reasonable cause. Written notification, documenting the reason for study suspension or termination, will be provided by the suspending or terminating party to investigator, funding agency, and/or regulatory authorities. If the study is prematurely terminated or suspended, the principal investigators will promptly inform the Institutional Review Board (IRB) and sponsor/funding agency and will provide the reason(s) for the termination or suspension. If the risks are not associated with POINT intervention recovery coaching services, participants may continue to receive them.

Circumstances that may warrant termination or suspension include, but are not limited to:

- Determination of unexpected, significant, or unacceptable risk to participants
- Insufficient compliance of study staff to the protocol (i.e., significant protocol violations)

The study may resume once concerns about safety, protocol compliance, and data quality are addressed, and satisfy the funding agency, sponsor, IRB, or other relevant regulatory or oversight bodies (DSMB).

#### 10.1.3 CONFIDENTIALITY AND PRIVACY

Responses to the structured interview questions will be entered by the recovery coach or research assistant into a form housed in REDCap. Only necessary research team members will have access to these data, and all accounts are password protected.

To protect the confidentiality of patients related to the secondary data, we will work with Regenstrief Institute (an honest broker who can act as a firewall between personally identifiable health data and the researchers) to develop a process for masking and merging the data that will ensure all data is stripped of personally identifying information before being delivered to the research team. Regenstrief will link hospital, government, substance abuse treatment, and structured interview data. We will only be asking for data to be delivered at a single time point, so there will be no need to link data longitudinally. Regenstrief will keep a key that will allow them to identify subjects; however, this key will not be shared with the researchers and will be destroyed at conclusion of the study; thus, researchers will never obtain an identifiable data set. The researchers will keep all data on a HIPPA compliant network/server behind a university firewall, and only those individuals who need access to the data will be able to obtain it using their login ID.

To protect confidentiality of all participants, we will assign each participant a subject identification number that will only be connected to the participants' names on a separate REDCap form, which will only be accessible by necessary research team members. We will store all complete informed consent documents in a locked file cabinet in a locked office. When REDCap data are extracted from the system to be sent to Regenstrief, they will be temporarily stored on a secure server behind a university firewall. They will be sent via a secure online sharing system that requires a password for download. Once accessed and downloaded by Regenstrief, these data will be deleted from the secure server. All grant personnel who are involved in the design or conduct of this research will have demonstrated successful completion of human subjects training, specifically Collaborative Institutional Training Initiative (CITI) Program.

To further protect the privacy of study participants, a Certificate of Confidentiality will be issued by the National Institutes of Health (NIH). This certificate protects identifiable research information from

forced disclosure. It allows the investigator and others who have access to research records to refuse to disclose identifying information on research participation in any civil, criminal, administrative, legislative, or other proceeding, whether at the federal, state, or local level. By protecting researchers and institutions from being compelled to disclose information that would identify research participants, Certificates of Confidentiality help achieve the research objectives and promote participation in studies by helping assure confidentiality and privacy to participants.

